Binary endpoints, including primary endpoint, are analyzed using Chi-2 test. Continuous data are assessed for parametric distribution and analyzed with Student's T-test on logarithmic transformed data in case of non-parametric distribution.

Level of statistical significance is set to 5%.

A logistic prediction model will be developed. Dependent variable is intubation. Independent variables are age (continuous), FLUS result (Binary or ordinal), SARS-CoV-2 status (Binary) and peripheral oxygen saturation (continuous).

The data set will be divided in two. One is used for model development and one is used for validation of the model. Geographic external validity is tested. Internal validity is tested with bootstrapping method. Sensitivity, specificity and ROC AUC is calculated.

Sample size

No prior publications are available for sample size estimation.

For the prediction model we wish to include 10-15 events per independent variable, 50-75 events. From early estimations about 20% of admitted patients requiring intubation our estimate is 375-400 participants.

Inclusion period

An end date is set to May 15 2020. If COVID-19 pandemic is ongoing at this time point the study may extent.

Blinding

Ultrasound film clips are analyzed blinded to other variables.

Plan for publication

Data analysis is estimated to end July 1. 2020. Article submission is estimated to October, 2020.

Preliminary data analysis

Available data will be analyzed soon after 15. May.

Ethical considerations

FLUS is without any risk to patients. COVID-19 is an infectious disease and isolation is needed. Contamination during the study needs to be avoided. For this reason, FLUS is only performed by the physicians who are required to see the patient regardless of this study. The ultrasound equipment is cleaned after each examination in accordance with local guidelines.

Legal regulations

In Denmark the study is classified as a quality assurance project. Arrangements and permission to access to patient files in each site is required. According to guidance from the legal office at Region Midt a data management agreement is not needed.

International data agreements are required to data transfer from international sites to Denmark.

All international sites must adhere to local regulation. Responsibility of this is on the international site.

Publication

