ITA admission	Univariat logistiscal regression	Variable: ita_in flusmed	
	Multivariate logistical regression	Variable: ita_in, Flusmed, alder, køn, sat	, if behandlingsloft_ita ==0
Ventilator treatment	Univariat logistical regression	Variable: respirator_beh flusmed	
	Multivariate logistical regression	Variable: respirator_beh Flusmed, alder, køn, sat	, if behandlingsloft_resp ==0

Continuous variables are assessed for parametric distribution with quartile-quartile plots. Medians, interquartile ranges or means and standard deviations and ranges are reported according to parametric distribution. Students' t-test or Mann-Whitney U test is used as it was considered appropriate to evaluate differences between groups. The statistical significance is set to 5%. All data are handled in Excel (Microsoft) and REDCap (hosted at Aarhus University). All analyses are performed using Stata 14.2 (StataCorp, USA).

Building Prediction Models

Prediction models are based on multivariable logistic regression and preselected variables. The variables are sex, age, relevant comorbidity, oxygen administration and the mean-FLUS score. The selection of these variables is based on published data and clinical experience available to the study group during the study design stage. Explanatory variables are examined to decide cut-points, scales or the need for transformation. Variables are limited and prioritized to avoid overfitting or underfitting, respecting the study population size. Every included variable require at least 15 events.

The dependent variable is the primary outcome of interest: the COVID-19-related need for mechanical ventilation in the main analysis. Secondary outcomes are analyzed using the same logistic regression model, except for the outcome on high-flow oxygen treatment. The explanatory variable on oxygen administration is considered closely related to the outcome and is thus excluded from this analysis.

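### The protocol's sample-size line does not follow from its own inputs: four named variables give 40–60 events, not 50–75, and 50–75 events at 20% need 250–375 participants, not 375–400

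*Protocol*

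**What the plan says.** The protocol's Sample size section sets the event target: "For the prediction model we wish to include 10-15 events per independent variable, 50-75 events". It then converts this to a number of patients: "From early estimations about 20% of admitted patients requiring intubation our estimate is 375-400 participants". No allowance for dropout or missing data is mentioned.

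The model is defined in the protocol's Data analysis section: "Independent variables are age (continuous), FLUS result (Binary or ordinal), SARS-CoV-2 status (Binary) and peripheral oxygen saturation (continuous"). That is four variables. The same section divides the data into a development part and a validation part, without giving the fractions.

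The SAP, under Building Prediction Models, has a different list: "The variables are sex, age, relevant comorbidity, oxygen administration and the mean-FLUS score". That is five variables. It also sets a floor: "Every included variable require at least 15 events". The sentence before the floor allows the set of variables to be cut and ranked to suit the size of the study population. The multivariate row for ventilator treatment in the SAP's table has yet another list, with four predictors: "respirator_beh Flusmed, alder, køn, sat" (mean FLUS score, age, sex, saturation).

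**The concern.** An events-per-variable calculation has two steps: multiply the events per variable by the number of variables, then divide by the event rate. The protocol gives every input, and neither step returns the printed figure. The protocol's range also starts at 10 events per variable, while the SAP's minimum is 15.

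These figures are the only stated basis for the size of the study and for how many predictors the ventilation model may carry. A reader cannot tell which variable count, which events-per-variable figure or which model the 375–400 participants are meant to support. If events fall short, the SAP floor removes variables, but neither document gives the order of removal. The adjustment set alongside FLUS would then be chosen with the data in hand.

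**Working it through.** **Inputs.** Protocol, Sample size: 10–15 events per variable, 50–75 events, event rate 20%, N = 375–400. Protocol, Data analysis: four variables. SAP, Building Prediction Models: at least 15 events per variable, five variables. SAP table, ventilator row: four variables.

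**Formulas.** Events = events per variable × number of variables. N = events ÷ event rate.

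**Step 1: the event target.**
- Four variables: 10 × 4 = 40 and 15 × 4 = 60, so 40–60 events.
- Five variables: 10 × 5 = 50 and 15 × 5 = 75, so 50–75 events.

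The printed range is reproduced exactly with five variables and not with the protocol's four.

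**Step 2: from events to participants at 20%.**
- 40–60 events: 40 ÷ 0.20 = 200 and 60 ÷ 0.20 = 300.
- 50–75 events: 50 ÷ 0.20 = 250 and 75 ÷ 0.20 = 375.

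The printed lower bound of 375 is the upper result of the five-variable calculation. The printed upper bound of 400 corresponds to 400 × 0.20 = 80 events, above the stated target. Going from 375 to 400 would take an unstated allowance of 6.25% (375 ÷ 0.9375 = 400). Going from 250 to 375 would take a loss of one third (1 − 250 ÷ 375 = 0.33), and nothing in the documents suggests that.

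**Step 3: what the printed N gives.** 375 × 0.20 = 75 and 400 × 0.20 = 80 events.
- Five variables: 75 ÷ 5 = 15 and 80 ÷ 5 = 16 per variable.
- Four variables: 75 ÷ 4 = 18.75 and 80 ÷ 4 = 20 per variable.

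**Step 4: the lower end against the SAP floor.** With 50 events, 50 ÷ 4 = 12.5 and 50 ÷ 5 = 10 per variable. Both are below 15. 50 ÷ 15 = 3.3, so three variables would comply.

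**Step 5: the data split.** The fractions are not given. With equal halves (an assumption), the development part has 37.5–40 events: 9.4–10 per variable for four variables, 7.5–8 for five. For the range over other splits, find the development share at which 15 events per variable still holds:
- Four variables (60 events): 60 ÷ 80 = 75% to 60 ÷ 75 = 80% of participants.
- Five variables (75 events): 75 ÷ 80 = 94% to 75 ÷ 75 = 100%.

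**The case against.** The strongest reply is that the planned N is sound and only its derivation is poorly written. 50–75 is exactly 10–15 × 5, five is the count in the SAP text, and 375 is exactly 75 ÷ 0.20. The authors probably counted five variables and set N on the stricter end. Much of this stands. At 20%, 375–400 participants meet the SAP floor for four or five single-parameter variables in the full data set. The protocol does not say that this is how N was reached, however, and its own variable list has four entries.

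Several stronger readings are tempting, and the documents do not support them:
- *That 50 events in itself breaks the SAP rule.* It does not. The SAP lets variables be limited, and three would comply. The conflict is with the four- and five-variable models actually named.
- *That the SAP requires 75 events.* Only its text list implies that. Its ventilator row has four predictors and implies 60.
- *That the target should be 60–90 events.* This needs the ordinal FLUS score to be entered as three indicators, giving six parameters. Neither document states that coding; an ordinal score can enter as one term, and the SAP uses a mean score.
- *That the SAP fits the full model to secondary outcomes regardless of event count.* It says: "Secondary outcomes are analyzed using the same logistic regression model, except for the outcome on high-flow oxygen treatment". This can be read as the same method under the same floor. For high-flow oxygen, oxygen administration is left out, so four variables remain.

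The protocol's primary endpoint is analysed with a chi-squared test, which these figures do not affect.

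**Conclusion.** The point holds as an inconsistency in the figures. The event target does not follow from the protocol's four variables (40–60, not 50–75). The participant range does not follow from the event target (250–375, not 375–400). The 10-per-variable lower end conflicts with the SAP's minimum of 15 for any model with four or five variables.

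A reader might infer that the study is too small. The documents do not show that: the printed N matches the 15-event end of a five-variable model and exceeds what four variables need. This rests on two conditions. The first is that events are counted in the full data set; after an equal split (assumed), about 38–40 remain for development. The second is the 20% rate, which the protocol gives for admitted patients although its inclusion criteria also take patients seen only for diagnostic work-up. At assumed overall rates of 10% and 15%, 375–400 participants would give 38–40 and 56–60 events.

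The correction is worth making because these figures support the main prediction model and cost almost nothing to put right.

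**What to change.** 1. Name one variable list for the ventilation model and use it in the protocol, the SAP text and the SAP table. The two four-variable lists also differ in content: the protocol has SARS-CoV-2 status where the ventilator row has sex.
2. Count the parameters in that list, including however many terms comorbidity takes, which the SAP leaves open.
3. Use the SAP's 15 events per parameter and restate the line at 20%: four parameters, 4 × 15 = 60 events and 300 participants; five parameters, 5 × 15 = 75 events and 375 participants. If 400 includes an allowance, say what it is for.
4. Delete the 10-per-variable and 50-event lower ends.
5. Say whether the event count refers to the full data set or the development part. If it is the development part, state the events per variable that this part really provides and reconcile that with the minimum of 15, rather than enrolling more patients.
6. State the order in which variables are dropped if events fall short. A penalised fit is an option for the authors but is not part of this correction.

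The cost is a few sentences in each document, with no change to data collection.

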Focused lung ultrasound for diagnosing and risk- stratification of patients with COVID-19 symptoms

April 8, 2020
NCT 04327674

Background

COVID-19 is defined as an infectious disease caused by SAR-CoV-2 virus. It results in pneumonia and sometimes respiratory failure. SARS-CoV-2 pandemic has led to massive strain on health care facilities. A large proportion of the population is at risk of COVID-19 and some estimates suggest that up to 15% will need hospitalization. Such number of patients strains the health care system to its maximum as capacity has limitations even in highly developed countries.

Early reports estimate that more than 80% of patients admitted to hospital with COVID-19 have abnormal findings on chest radiographs¹. Thus, imaging seems to be an important part of the diagnostic work-up. In most hospitals however, access to CT-scanning of the thorax of all patients with COVID-19 or with suspicion of COVID-19 is unrealistic due to restricted capacity. Chest radiographs are faster and easier to do, but may require transportation of the patient to the department of radiology which carries a risk of virus spreading in the hospital. On-site chest radiograph is often of such low quality that diagnosis or follow-up will be difficult.

Focused ultrasound examination of the lungs, FLUS, is a diagnostic tool that can show changes in the lung parenchyma due to pneumonia. FLUS is a bed-side examination performed by the physician which results in reduced risk of in-hospital virus contamination. Furthermore, results from FLUS are immediately available to the physician. This allows rapid decision-making which is essential in cases of high patient burdens as seen in the COVID-19 pandemic.

Furthermore, SARS-CoV-2 positive patients with pneumonia may be at higher risk of respiratory failure than those without pneumonia. Identifying patients at high risk can qualify decisions about monitoring level and organization of intensive care resources. Conversely, patient with COVID-19 symptoms but without pneumonic FLUS finding could likely be managed as out-patients. Such a risk-stratification may optimize the allocation of limited healthcare resources and reserve in-hospital capacity to those patients who needs it.

Hypothesis

FLUS can risk-stratify patients with COVID-19 symptoms.

FLUS can predict respiratory failure in patients with COVID-19 pneumonia.

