FLUS can diagnose COVID-19 pneumonia with high sensitivity and specificity using PCR-test and chest radiograph as reference.

Aim

To study the ability of FLUS in COVID-19 to predictive respiratory failure.

To study the diagnostic capability of FLUS to find COVID-19 pneumonia.

To study risk-stratifying capability of FLUS in patients with COVID-19 symptoms.

Method

Design

Multicenter prospective cohort study with convenience sampling.

Setting

Emergency departments or internal medicine departments who admit patients with COVID-19 symptoms.

Participants

Patients who have COVID-19 symptoms and require diagnostic testing.

Patients who have a positive SAR-CoV-2 PCR-test and require admission to hospital.

Inclusion criteria

- Patients who are seen in COVID-clinics or emergency departments due to symptoms that require diagnostic work-up to COVID-19.
- Patients admitted to hospital with positive SARS-COV-2 PCR-test and in whom FLUS is performed less than 48 hours after admission.

Exclusion criteria

- Age less than 18 year.
- Former participation in this study.
- Pre-FLUS ventilator support.

Double inclusion

Inclusion in this study will not restrict patient from inclusion in other studies.

Recruitment

Participants are recruited at the local hospital. In Denmark the study is labelled quality assurance and the need for informed consent is thus waived. Local regulations are followed and it is the responsibility of each inclusion site to achieve appropriate regulatory permissions including need for approval from local ethical committees and healthcare authorities.

Variables

Ultrasound variables: FLUS are performed according to ERS guidelines and to Standard of Operating Procedure specific to this study. Film clips are recorded and saved for later evaluation. 14 zones are scanned. Film clips are marked with scanning position (L1, L2...etc.). If the patient is unable to sit, only anterior and lateral zones are scanned. FLUS findings are assessed on the film clips by an observer blinded to other variables. Findings are coded with 1/0 for presence of pneumonia. Moreover, a scoring system is applied:

FLUS findings	Score
Normal FLUS	0
Interstitial syndrome, defined as more than 3 B-lines in a single zone.	1
Diverse B-lines or irregular pleura	
Interstitial syndrome, defined as more than 3 B-lines in a single zone.	2
Confluent B-lines.	
Consolidations (sub-pleurale, lobar, with or without air-bronchograms)	3

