Data on FLUS operator: Level of medical degree. Years of experience with lung ultrasound. Completed training in FLUS.

From patient files the following data is extracted:

Patient demographic: Sex, age, height, weight, co-morbidities.

Clinical data on time of admission: Blood pressure, pulse, peripheral saturation, respiratory frequency, temperature, length of illness, list of symptoms, limitation to treatment i.e. not suited or willing to intensive care treatment and intubation.

Data from radiographic diagnostics: Result of chest radiograph, CT or HRCT scanning, if done for clinical reasons. No further review of radiographic examinations is performed. Results given by local radiology department is used.

Microbiological data: Result of SARS-CoV-2 PCR-test from nasal/oral/laryngeal or tracheal samples.

Data from admission: Time of admission. Place of admission. Time of dismissal. Admission to intensive care. Intubation. Time in ventilator. Death, survival. In hospital survival, 14- and 30-days survival.

Endpoints

Primary endpoint: FLUS (binary: positive/negative pneumonia) related to intubation (yes/no).

Secondary endpoints: Relationship between FLUS and SARS-CoV-2 PCR result.

Relationship between FLUS and radiographic findings.

Relationship between FLUS and admission to intensive care (not intubation).

Relationship between FLUS and re-admission (Patient returning to emergency department or COVID-clinic).

Scores of FLUS findings in different zones.

Data management

The study uses convenience sampling as FLUS may not be available at all times. FLUS is performed by the clinician such that only doctors with clinically relevant work are allowed to scan the patient. This minimizes the risk of disease transfer to doctors and reduces the use of protection equipment.

Ultrasound film clips are recorded according to standard operating procedure. Film clips are stored securely, according to local legal regulations. All variables extracted from patient files are stored in an eCRF using REDCap supplied by Aarhus University Hospital.

Every site will have access to enter data in data capture instruments. Access to REDCap is managed by the project steering committee at Aarhus University Hospital.

Data analysis

All data are analyzed in Stata.

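### The sample size applies an intubation rate stated for admitted patients to all 375-400 participants, although patients who need not be admitted are also enrolled

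*Protocol*

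**What the plan says.** The Sample size section of the protocol aims for 10-15 events per independent variable, which it gives as 50-75 events in total. It then says: "From early estimations about 20% of admitted patients requiring intubation our estimate is 375-400 participants". The event is intubation, the dependent variable of the prediction model under Data analysis.

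The protocol's Inclusion criteria admit two groups to the study. One is patients already in hospital with a positive PCR test. The other is "Patients who are seen in COVID-clinics or emergency departments due to symptoms that require diagnostic work-up to COVID-19", and for this group admission is not a condition. The Background section foresees that some such patients might not be admitted: "Conversely, patient with COVID-19 symptoms but without pneumonic FLUS finding could likely be managed as out-patients". The Endpoints section includes a secondary endpoint for patients who come back to the emergency department or COVID-clinic.

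The SAP, under Building Prediction Models, requires at least 15 events for every variable in the model. Its text there lists five kinds of predictor: "The variables are sex, age, relevant comorbidity, oxygen administration and the mean-FLUS score". Its table row for ventilator treatment lists four: "respirator_beh Flusmed, alder, køn, sat". It adds: "Variables are limited and prioritized to avoid overfitting or underfitting, respecting the study population size".

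**The concern.** The rate and the number it produces refer to different populations. The 20% is a rate among admitted patients, while 375-400 is a count of all participants, some of whom may never be admitted. Unless nearly everyone is admitted, the study should expect fewer intubations than the 75-80 that the calculation implies.

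The number of intubations limits how many predictors the model can hold. If it falls below plan, either the model carries more predictors than the events support, or predictors are dropped by a choice made after the data have been seen. Neither document gives an expected admitted share, a quota of admitted patients or a rule to continue until a number of events is reached. Inclusion may be extended, but the protocol ties this to whether the pandemic is ongoing, not to an event count.

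**Working it through.** **Inputs.** From the protocol's Sample size section: intubation rate 0.20, stated for admitted patients; target 50-75 events; N = 375-400. From the SAP's Building Prediction Models: 15 events per variable. The admitted share *a* is not given and is varied below.

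**Assumptions.** Participants who are never admitted contribute no intubations. The 20% holds for every admitted participant, including those admitted with a negative PCR test, for whom the documents give no rate. Intubation in the protocol and ventilator treatment in the SAP are counted as the same event.

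**Step 1: reproduce the plan's figure.** N = events / rate. 75 / 0.20 = 375, the lower stated figure, and 400 x 0.20 = 80. The lower target would need only 50 / 0.20 = 250. The stated range is therefore sized on the upper target with the 20% applied to all participants.

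**Step 2: admitted share needed.** *a* = events / (0.20 x N).

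| Expected events | Where the number comes from | N = 375 | N = 400 |
|---|---|---|---|
| 40 | four predictors at 10 each | 53.3% | 50% |
| 50 | protocol's minimum | 66.7% | 62.5% |
| 60 | four predictors at 15 each | 80% | 75% |
| 75 | protocol's upper target; five predictors at 15 each | 100% | 93.75% |

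Four predictors is the number in the protocol's model and in the SAP's ventilator row. Five is the number in the SAP's text if relevant comorbidity counts as one.

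**Step 3: expected events by admitted share.** Events = N x *a* x 0.20. Predictors supported = events / 15, rounded down. The last column is the binomial probability, with N trials and probability 0.20 x *a*, of seeing at least 50 events.

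| Admitted share | Events, N = 375 / 400 | Predictors at 15 each | Chance of at least 50 events |
|---|---|---|---|
| 100% | 75 / 80 | 5 / 5 | above 99% |
| 90% | 67.5 / 72 | 4 / 4 | 99.4% / 99.9% |
| 75% | 56.25 / 60 | 3 / 4 | 83.5% / 93.2% |
| 50% | 37.5 / 40 | 2 / 2 | 2.3% / 6.0% |

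The predictor counts use events in the whole cohort and are therefore upper limits if the model is fitted to only part of it.

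**The case against.** The strongest reply is that the plan has slack and a safeguard. The size is set on 75 events while the stated minimum is 50, so an admitted share down to about 63-67% still gives the minimum in expectation. At 75% admitted, the chance of at least 50 events is 83-93%. The SAP's events-per-variable rule and its sentence on limiting variables mean that too few events should produce a smaller model, not an overfitted one. The protocol also calls its figure an estimate and says that no prior publications were available.

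Most of this stands, and it limits the point. It does not remove it. The slack exists at 10 events per variable, whereas the SAP asks for 15, which makes 60 or 75 the relevant count for four or five predictors. The safeguard names no order in which predictors give way.

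A second reply is that a large non-admitted share is not evident. The setting is departments that admit such patients, much of the data collection concerns the admission, and the Background sentence on out-patients describes a possible use of FLUS, not the enrolled cohort. This too is fair. It means that the documents do not establish a low share such as 50%. They do not establish a share near 100% either, because COVID-clinic patients are eligible without admission.

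A reader might infer more from the protocol's plan to divide the data set in two. With equal halves, which is an assumption because no ratio is given, the development half has 37.5-40 events and supports only two predictors at 15 each, even when everyone is admitted. That limit comes from the division and not from the admitted share, so it is not part of the size of this point. The differing SAP predictor lists and the SAP's restriction of the ventilator model to patients without a treatment restriction are likewise separate matters.

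**Conclusion.** The point holds as a sample-size assumption: a rate for admitted patients is applied to a population that need not be admitted. It should be corrected. Under the assumptions listed, the minimum of 50 expected events requires at least about 63-67% admitted, and the upper target of 75 requires at least 94-100%. At the SAP's 15 events per variable, four predictors require 75-80% admitted. An intubation in a patient first sent home and never counted as admitted would lower these shares slightly. A rate below 20% among admitted PCR-negative patients would raise them.

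Three stronger readings are not supported:

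- A reader might infer an arithmetic error. There is none, because 75 / 0.20 is 375.
- A reader might infer that the study will miss its event target. The admitted share is not stated, so the shortfall may be slight or serious.
- A reader might infer that 50-75 is a false forecast. It is worded as a target. What is overstated is the implied expectation of 75-80 events.

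Confidence is high in the mismatch. It does not extend to the size of its consequence.

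**What to change.** Keep N = 375-400 and keep 50-75 events as the target. Beside the target, replace the implied 75-80 expected events with N x admitted share x 20% over a stated range of shares: for example 75-80 at 100%, 68-72 at 90%, 56-60 at 75% and 38-40 at 50%. For each, state how many predictors are supported at 15 events per variable, counting only events in the data actually used to fit the model. Fix in advance, in the SAP, the order in which predictors are dropped if events fall short.

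The cost is one restated paragraph in the protocol, a short addition to the SAP on the dropping order, and a less favourable expected event count. No extra patients are needed.
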